1 INTRODUCTION

The statistical analysis plan (SAP), version 1.0, for the study with protocol number NPC-21-2 was finalized on 29 March 2023.

The final database lock for this study was on 30 March 2023 with last signature data lock approval on 03 April 2023. Further updates to the planned analysis are documented in this addendum.

Summary of changes:

- Updated the analysis methods of some secondary and exploratory endpoints

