1 INTRODUCTION

The purpose of this Statistical Analysis Plan (SAP) is to provide a description of the statistical methods to be implemented for the analysis of data for Nobelpharma Co., Ltd. protocol NPC-21-2 (Version 5.0; 18 October 2021). The SAP will be finalized prior to database lock. Any deviations from the SAP after database lock will be documented in the final Clinical Study Report (CSR).

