3.4.1 Primary Efficacy Analysis

The proportion of patients with the occurrence of CMV disease (CMV syndrome [see Appendix C of the protocol for definition of CMV syndrome] or tissue-invasive CMV disease [see Appendix D of the protocol for definitions of CMV disease]) or CMV viremia (defined as the detection of ≥ 250 IU/mL in plasma measured by PCR analysis in central laboratory or meets the local criteria for CMV viremia measured by PCR analysis or antigenemia testing) by Week 16 will be summarized by treatment group.

The 2-sided 95% exact Clopper-Pearson confidence intervals of the proportions will be provided. For any two treatment groups, the proportion difference and 95% unstratified Miettinen-Nurminen (score) confidence limits will be presented.

Comparisons across placebo and 6 mg/kg NPC-21 treatment group will use logistic regression analysis with stratification factor of region (United States or Japan) as a covariate

Non-responders will include all patients who develop CMV disease or CMV viremia. In principle, patients who discontinue from the study prior to Week 16 in the absence of CMV disease or CMV viremia will be considered as non-responders. If warranted under special circumstances, a patient who discontinues from the study prior to Week 16 may be discussed with the medical expert to determine status as a responder or non-responder. If this occurs, the rationale for considering the patient as a responder will be finalized before database lock and documented in this SAP. Sensitivity analysis may be performed to assess the impact of these patients on analysis results.

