3.4.2 Secondary Efficacy Analysis

3.4.2.1 Categorical Endpoints

The categorical endpoints as below will be analyzed using the same analysis method as primary analysis:

- Incidence of CMV disease or CMV viremia by Week 28
- Incidence of CMV disease by Week 16
- Incidence of CMV disease by Week 28
- Incidence of CMV viremia by Week 16
- Incidence of CMV viremia by Week 28
- Incidence of anti-CMV therapy during the Rescue Phase

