3.4.3 Exploratory Analysis

As the exploratory analysis, incidence of CMV disease or CMV viremia by Week 16 assessed by Endpoint data reviewers will be analyzed using the method described in Section 3.4.1. In addition, the below endpoints will also be analyzed.

- Incidence of CMV disease or CMV viremia by Week 28
- Incidence of CMV disease by Week 28
- Incidence of CMV viremia by Week 28

In addition, the Endpoint data reviewer findings will be listed by-patient.

As the supportive analysis, only criteria using the detection of ≥ 250 IU/mL in plasma measured by PCR analysis in central laboratory will be considered for the analysis of primary efficacy endpoint in Section 3.4.1. Non-responders will include all patients who have central CMV DNA assessments ≥ 250 IU/mL by Week 16. Patients who discontinue from the study prior to Week 16 in the absence of central CMV DNA assessments ≥ 250 IU/mL will be considered as non-responders.

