A complete physical examination will be performed at Screening; prior to study drug administration on dosing days (Day 1 and at Weeks 4, 8, and 12); within 1 hour of the end of the infusion on Day 1; at Weeks 1, 2, 3, 16, 20, 24, and 28; and at the initiation of the Rescue Phase. A physical examination may be performed by home healthcare services at non-dosing day visits.

The physical examination will be presented in a by-patient listing.

3.7.6 *Data Safety Monitoring Board*

The Data Safety Monitoring Board (DSMB) will meet to review unblinded aggregate and individual patient data related to safety, data integrity, and overall conduct of the study and will provide recommendations to continue, temporarily halt, modify, or terminate the study based on data analysis. The committee may communicate other recommendations or concerns as deemed appropriate. Additional information will be provided in the DSMB charter as approved by the members.

3.8 **Interim Analysis**

No interim analysis is planned.

4 **CHANGES FROM PROTOCOL-SPECIFIED STATISTICAL ANALYSES**

In Section 3.4.2.2 for secondary efficacy analysis, the below secondary analysis was added compared to protocol:

- Duration of the detection of CMV DNA ≥ 250 IU/mL in plasma measured by PCR analysis in central laboratory.

The section 3.4.3 was added as the exploratory analysis to the endpoints.

5 **PROGRAMMING SPECIFICATIONS**

Analyses will be performed using SAS® version 9.3 or higher. All available data will be presented in patient data listings which will be sorted by patient and visit date as applicable. Detailed Programming Specifications will be provided in a separate document.

STATISTICAL ANALYSIS PLAN ADDENDUM

Protocol Title: A Phase 2, Randomized, Double-Blind, Placebo-Controlled Study of NPC-21 for Kidney Transplant Recipients at High-Risk of Cytomegalovirus Infection (LionHeart21)

Protocol Number: NPC-21-2

Protocol Version/Date: Version 5.0/18 October 2021

Investigational Product: NPC-21

Sponsor: Nobelpharma Co., Ltd.
[name]
[name]
[contact]
[contact]

SAP Version/Date: Version 1.0/29 March 2023

SAP Addendum Version/Date: Version 1.0/15 May 2023

CONFIDENTIAL

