2 DATA ANALYSIS CHANGES

2.1 Categorical Endpoints

In SAP version 1.0, section 3.4.2.1 describes that the categorical endpoints are analyzed using the same analysis method as the primary endpoint.

However, for the analysis of primary endpoint, the non-responders include all patients who develop CMV disease or CMV viremia and patients who discontinue from the study prior to Week 16 in the absence of CMV disease or CMV viremia.

This SAP addendum further clarifies that for the endpoints below, patients who discontinued from the study prior to Week 16 in the absence of CMV disease would not be considered as non-responders:

- Incidence of CMV disease by Week 16
- Incidence of CMV disease by Week 28

For the endpoints below, patients who discontinued from the study prior to Week 16 in the absence of CMV viremia would not be considered as non-responders:

- Incidence of CMV viremia by Week 16
- Incidence of CMV viremia by Week 28

For the secondary endpoint “Incidence of CMV disease or CMV viremia by Week 28”, the same analysis method as the primary endpoint is used by still including patients who discontinued from the study prior to Week 16 in the absence of CMV disease or CMV viremia as non-responders.

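### An addendum dated 46 days after database lock withdraws the drop-out rule from six secondary and exploratory endpoints, without stating blinding status or how drop-outs are then counted

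*SAP*

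**What the plan says.** **Timing.** SAP Section 1 sets the standard: "The SAP will be finalized prior to database lock". It adds that departures made after lock will be recorded in the clinical study report (CSR). According to Section 1 of the addendum, SAP v1.0 "was finalized on 29 March 2023", and "The final database lock for this study was on 30 March 2023 with last signature data lock approval on 03 April 2023". The addendum's cover details read "SAP Addendum Version/Date: Version 1.0/15 May 2023".

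**Rule in SAP v1.0.** For the primary endpoint, Section 3.4.1 gives this as its general rule: "patients who discontinue from the study prior to Week 16 in the absence of CMV disease or CMV viremia will be considered as non-responders". It allows a discontinued patient to be classed as a responder only in special circumstances, with the reasons settled before lock. Section 3.4.2.1 extends the approach to the secondary endpoints: "The categorical endpoints as below will be analyzed using the same analysis method as primary analysis". Section 3.4.3 says that the Week 16 composite, as judged by the endpoint data reviewers, "will be analyzed using the method described in Section 3.4.1". It then adds three Week 28 endpoints.

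**Rule in the addendum.** Section 2.1 states "This SAP addendum further clarifies that for the endpoints below, patients who discontinued from the study prior to Week 16" without CMV disease are no longer non-responders for CMV disease by Weeks 16 and 28. A parallel sentence covers CMV viremia by Weeks 16 and 28. Section 2.2 does the same for the exploratory CMV disease and CMV viremia endpoints by Week 28. Both sections keep the non-responder rule for the composite of disease or viremia.

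**The concern.** A rule for handling drop-outs that is settled after lock can no longer be shown to be independent of the data. The plan itself recognises this. Section 3.4.1 requires single-patient exceptions to the rule to be settled before lock, and Section 3.2.3 requires the Per Protocol exclusion list to be final before unblinding. The addendum removes the rule for whole endpoints after lock, gives no scientific reason, and in the available text carries no comparable safeguard.

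The affected endpoints are not merely tabulated. Through Section 3.4.2.1 they receive the primary method, including the confidence limits for the difference and the region-adjusted logistic regression. The drop-out rule therefore feeds into estimates and p-values as well as raw percentages. If drop-out differs between arms, it can move the treatment difference in either direction.

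**Working it through.** **1. Dates.** From 30 March to 15 May 2023 is 1 + 30 + 15 = 46 days. From the last lock signature on 3 April it is 27 + 15 = 42 days.

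**2. Endpoints affected.** CMV disease and CMV viremia by Weeks 16 and 28 (2 × 2 = 4 secondary), plus reviewer-assessed disease and viremia by Week 28 (2 exploratory), make 6.

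**3. Change or clarification?** The addendum's own reading of v1.0 answers this. Section 2.1 says that v1.0 put the categorical endpoints under the primary method. Section 2.2 says the same of all four exploratory endpoints. Each then takes the drop-out rule away. On that reading the rule was in force and was removed.

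**4. Planning inputs.** Protocol 10.2.7 and SAP 2.2.4 give 30% vs 60% events, 15% early discontinuation, two-sided 0.05, 80% power and 48 patients per arm. The unpooled two-proportion formula reproduces the 48:

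(1.960 + 0.842)² × (0.24 + 0.21) / 0.30² = 39.24, rounded up to 40; 40 / 0.85 = 47.06, rounded up to 48.

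The addendum does not affect this figure. Drop-out of 15% is 0.15 × 48 = 7.2, or about 7 patients per arm.

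**5. Size of the change.** The documents give no rates for disease or viremia separately, so the composite's 60% and 30% are borrowed as an illustration. Let p be the event rate among patients who stay and d the drop-out proportion, with every drop-out leaving before any event:

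- v1.0 rule: d + (1 − d)p
- Addendum rule, drop-outs counted event-free: (1 − d)p
- Addendum rule, drop-outs excluded: p

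Both addendum rows are needed because its wording fits either counting. Rates are placebo vs NPC-21.

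| Drop-out, placebo / NPC-21 | v1.0 rule | Event-free | Excluded |
|---|---|---|---|
| 15% / 15% | 66.0% vs 40.5%, difference 25.5 | 51.0% vs 25.5%, difference 25.5 | 60% vs 30%, difference 30 |
| 10% / 20% (assumed) | 64% vs 44%, difference 20 | 54% vs 24%, difference 30 | 60% vs 30%, difference 30 |
| 20% / 10% (assumed) | 68% vs 37%, difference 31 | 48% vs 27%, difference 21 | 60% vs 30%, difference 30 |

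With equal drop-out, event-free counting leaves the difference at 25.5 points. The risk ratio still moves, from 40.5 / 66.0 = 0.61 to 25.5 / 51.0 = 0.50.

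**6. A rarer endpoint.** Assume 10% vs 5% for CMV disease, with 15% drop-out in both arms. The v1.0 rule gives 0.15 + 0.85 × 0.10 = 23.5% vs 0.15 + 0.85 × 0.05 = 19.3%, a ratio of 0.82. Event-free counting gives 8.5% vs 4.3%, a ratio of 0.50. The rarer the event, the more the drop-out rule decides the result.

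**The case against.** **The addendum is open about being a change.** Its Section 2 heading speaks of changes, its summary says methods were updated, and it prints both lock dates. SAP Section 1 promises that post-lock deviations will appear in the CSR. This stands. The fault is inconsistent labelling, because the operative sentences speak of clarifying. A reader might infer that the results are being passed off as planned. The documents do not support that, since they contain no results and no CSR.

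**SAP v1.0 was not fully clear.** The rule in Section 3.4.1 is worded for the composite and reaches the components only by cross-reference. Section 3.1.5 says that efficacy data are in general not imputed. Section 3.4.3 does not restate the method for its Week 28 endpoints, and the protocol (10.2.1) plans only descriptive summaries beyond the primary endpoint. This stands in part: calling it the reversal of an unmistakable rule goes too far. But Section 3.1.5 is a general default, Section 3.4.1 is specific, and the addendum itself reads v1.0 as applying the primary method.

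**The new rule may be the better one.** Under v1.0 every early drop-out becomes a CMV disease case, which pulls the risk ratio of a rare endpoint towards 1. This stands, and it is a reason not to insist that v1.0 must lead.

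**Nothing shows that the choice followed the data.** This also stands. A reader might infer from the dates that the rule was picked with treatment assignments in view. The documents give no unblinding date in either direction, and part of the addendum's front matter is not in the public text.

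**Conclusion.** The point holds as one about timing, labelling and definition. The documents establish that the drop-out rule for six endpoints was changed 46 days after lock, that the addendum describes this inconsistently, and that the available text is silent on blinding status and on how drop-outs are counted. They do not establish a data-driven choice. The primary endpoint and the composites are unaffected, and the six endpoints are secondary or exploratory in a Phase 2 trial.

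Under the illustrative rates, equal 15% drop-out shifts each arm's incidence by 15 points with event-free counting and leaves the difference at 25.5 points. Exclusion widens the difference to 30. With the assumed 10-point imbalances, the difference moves from 20 to 30 under either counting, or from 31 to 21 (event-free) or 30 (excluded). These sizes rest on borrowed composite rates, assumed drop-out imbalances and all drop-outs leaving before any event. The actual effect depends on drop-out by arm and on component rates that the documents do not give.

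**What to change.** For the six endpoints:

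- Report the v1.0 rule and the addendum rule side by side, and label the addendum rule in both the addendum and the CSR as changed after database lock (post hoc). Which of the two is shown first is a matter of judgement.
- State whether treatment codes had been released to anyone involved in the decision before 15 May 2023.
- State whether drop-outs count as event-free or leave the denominator. The same sentence should cover patients who leave between Weeks 16 and 28, whom the addendum does not mention.

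The cost is one extra set of tables, a few sentences and a post hoc label on some results. It is a cheap improvement: readers can see how much the choice matters and need not take it on trust.

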2 DATA ANALYSIS CHANGES

2.1 Categorical Endpoints

In SAP version 1.0, section 3.4.2.1 describes that the categorical endpoints are analyzed using the same analysis method as the primary endpoint.

However, for the analysis of primary endpoint, the non-responders include all patients who develop CMV disease or CMV viremia and patients who discontinue from the study prior to Week 16 in the absence of CMV disease or CMV viremia.

This SAP addendum further clarifies that for the endpoints below, patients who discontinued from the study prior to Week 16 in the absence of CMV disease would not be considered as non-responders:

- Incidence of CMV disease by Week 16
- Incidence of CMV disease by Week 28

For the endpoints below, patients who discontinued from the study prior to Week 16 in the absence of CMV viremia would not be considered as non-responders:

- Incidence of CMV viremia by Week 16
- Incidence of CMV viremia by Week 28

For the secondary endpoint “Incidence of CMV disease or CMV viremia by Week 28”, the same analysis method as the primary endpoint is used by still including patients who discontinued from the study prior to Week 16 in the absence of CMV disease or CMV viremia as non-responders.

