2.2.4 Sample Size Determination

A total sample size of approximately 108 patients is planned for the study, with a 1:1 randomization ratio for 6 mg/kg NPC-21 versus placebo and another 12 patients for high-level dose of 12 mg/kg NPC-21 (4:1:4 randomization ratio for 6 mg/kg NPC-21, 12 mg/kg NPC-21, or placebo). The sample size calculation is based on the modified Intent-to-Treat (mITT) Population from the first dose of NPC-21 through Week 16 for the occurrence of CMV disease (CMV syndrome or tissue-invasive CMV disease) or CMV viremia (defined as the detection of ≥ 250 IU/mL in plasma measured by PCR analysis in central laboratory or meets the local criteria for CMV viremia measured by PCR analysis or antigenemia testing) primary endpoint. Assuming an early discontinuation rate of 15%, approximately 48 patients each in the 6 mg/kg NPC-21 and placebo arms are needed with a 2-sided significance level of 0.05 and a power of 80% to detect a difference between NPC-21 at a predicted incidence rate of CMV disease (CMV syndrome or tissue-invasive CMV disease) or CMV viremia of 30% versus 60% for placebo. In addition, a sample size of 12 patients for the 12 mg/kg NPC-21 arm is considered adequate for the planned exposure-response analysis.

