3.4.2.3 Time-to-Event Endpoints

The time-to-event endpoints include:

- Time to detectable CMV disease or CMV viremia by Week 28
- Time to detectable CMV disease by Week 28
- Time to detectable CMV viremia by Week 28

For each time-to-event endpoint, the count and proportion of patients experiencing event and censored will be summarized by treatment group. The Kaplan-Meier estimate of median time and Brookmeyer-Crowley 95% confidence intervals will be presented. Log-rank test will be used to test whether there is significant difference among groups.

The endpoints will be calculated as:

- Time to detectable CMV disease or CMV viremia by Week 28 (Weeks) = (Date of CMV disease or CMV viremia – first dose date of study drug + 1)/7.
- Time to detectable CMV disease by Week 28 (Weeks) = (Date of CMV disease – first dose date of study drug + 1)/7.
- Time to detectable CMV viremia by Week 28 (Weeks) = (Date of CMV viremia – first dose date of study drug + 1)/7.

If patients experience CMV disease or CMV viremia, the dates of entering Rescue Phase will be used to determine the date of CMV disease or CMV viremia and the patients will not be censored. Patients who do not experience CMV disease or CMV viremia will be censored at the latest CMV viremia assessments.

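### After the SAP addendum, event-free leavers before Week 16 fail the composite but not its components, so viremia incidence on the mITT denominator is a lower bound and its gap to the composite is almost all drop-out.

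*SAP*

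**What the plan says.** For the primary composite by Week 16, SAP 3.4.1 sets this rule, with exceptions allowed: "patients who discontinue from the study prior to Week 16 in the absence of CMV disease or CMV viremia will be considered as non-responders". SAP 3.4.2.1 applied the same method to all categorical secondary endpoints.

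Addendum 2.1 changes this for the components. For CMV viremia by Weeks 16 and 28, "patients who discontinued from the study prior to Week 16 in the absence of CMV viremia would not be considered as non-responders"; a parallel sentence covers CMV disease. The Week 28 composite keeps the primary method "by still including patients who discontinued from the study prior to Week 16 in the absence of CMV disease or CMV viremia as non-responders". Addendum 2.2 repeats the split for the Week 28 endpoints assessed by the endpoint data reviewers. The Week 16 composite stays under SAP 3.4.1.

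The addendum does not give the denominator for the components. SAP 3.2.2 assigns the mITT Population to all efficacy analyses. SAP 3.1.5 says that efficacy data are in general presented as observed, without imputation.

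Two other analyses treat the same patients in their own way:

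- SAP 3.4.2.3 (time-to-event): "Patients who do not experience CMV disease or CMV viremia will be censored at the latest CMV viremia assessments".
- SAP 3.4.3, supportive analysis on central PCR alone: event-free leavers before Week 16 are failures. The addendum amends only the first paragraph of 3.4.3, so this rule stands.

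**The concern.** Readers look at the components to see what drives a composite. Here one patient, gone before Week 16 with no CMV event seen, is a failure in the composite and, on the mITT reading, event-free in both components. The components then cannot be reconciled with the composite they form.

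Two things follow for viremia. Its reported incidence counts unobserved time as infection-free, so it is a floor. The excess of composite over viremia also invites a clinical explanation, such as CMV disease without viremia, when it is mostly early departure. Protocol Appendix C requires CMV detection in blood for CMV syndrome, so little disease without viremia is to be expected.

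**Working it through.** **Inputs.** SAP 2.2.4 gives the planning rates, "CMV viremia of 30% versus 60% for placebo", with equal allocation between those two arms, and states: "Assuming an early discontinuation rate of 15%, approximately 48 patients each in the 6 mg/kg NPC-21 and placebo arms are needed". The 15% covers all early discontinuation. The event-free share and the separate disease rate are not given, so both are assumptions below.

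**1. The plan's own figure.** With unpooled variance, n = (1.960 + 0.842)² × (0.3×0.7 + 0.6×0.4) / 0.3² = 39.2, so 40; 40/0.85 = 47.1, so 48 per arm. This reproduces. (Pooled variance gives 42, then 50.)

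**2. Structure.** On the mITT denominator, if every CMV event includes viremia:

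- viremia = observed events
- composite = observed events + event-free leavers
- gap = event-free leavers

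**3. Main scenario.** Constant event hazard; 15% leave, independently of outcome, at a uniform time in Weeks 0–16. With L = −ln(1−p), the chance that a leaver is still event-free on leaving is p/L.

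- 6 mg/kg: L = 0.357, p/L = 0.841. Event-free leavers 0.15×0.841 = 12.6%. Observed events 0.85×0.30 + 0.15×0.159 = 27.9%. Composite 0.85×0.30 + 0.15 = 40.5%.
- Placebo: L = 0.916, p/L = 0.655. Event-free leavers 0.15×0.655 = 9.8%. Observed events 0.85×0.60 + 0.15×0.345 = 56.2%. Composite 0.85×0.60 + 0.15 = 66.0%.

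| | 6 mg/kg | Placebo | Difference |
|---|---|---|---|
| True incidence | 30% | 60% | 30 |
| Viremia as reported | 27.9% | 56.2% | 28.3 |
| Composite as reported | 40.5% | 66.0% | 25.5 |
| Viremia understated by | 2.1 | 3.8 | |
| Composite minus viremia | 12.6 | 9.8 | |

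**4. Range.** Now take a constant drop-out hazard μ beside the event hazard λ (time unit 16 weeks), with μ set so that the event-free leaving share d = μ/(λ+μ) × [1 − e^−(λ+μ)]. Observed events are λ/(λ+μ) × [1 − e^−(λ+μ)].

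| d | 6 mg/kg observed (understated by) | Placebo observed (understated by) |
|---|---|---|
| 5% | 29.2% (0.8) | 58.0% (2.0) |
| 10% | 28.3% (1.7) | 56.0% (4.0) |
| 15% | 27.4% (2.6) | 54.0% (6.0) |
| 20% | 26.5% (3.5) | 51.9% (8.1) |

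Here d is the event-free share itself, so its 15% row is more severe than step 3, where 15% is everyone who leaves.

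**5. If leavers are excluded instead.** At d = 15% under step 4, viremia is 0.274/0.85 = 32.2% and 0.540/0.85 = 63.5%. These are slightly high, and the denominator differs from the composite's.

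**6. CMV disease.** Take the simplest case, drop-out at the start with d = 15%, and disease as 10–50% of composite events. The drop-out share of the composite-minus-disease gap is:

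- placebo: 0.15/(0.660 − 0.051) = 24.6% to 0.15/(0.660 − 0.255) = 37.0%
- 6 mg/kg: 0.15/(0.405 − 0.0255) = 39.5% to 0.15/(0.405 − 0.1275) = 54.1%

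At d = 5% the shares are 9–15% and 16–26%. The rest is viremia without disease.

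**7. The supportive analysis.** If nearly all events are central-PCR positive, the central-PCR analysis in SAP 3.4.3 would give about 40.5% at Week 16 in the 6 mg/kg arm. The broader viremia endpoint, which admits central or local criteria, would give 27.9%. The narrower definition would report the higher incidence.

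**The case against.** Counting a leaver as failing a prevention composite without labelling that patient a CMV disease case is defensible, and the SAP 3.4.2.1 rule would have done the labelling. The addendum states its rule openly. These endpoints are secondary, and Protocol 10.2.1 summarises them descriptively. The understatement in the main scenario is about one patient in 48 on 6 mg/kg (0.021×48 = 1.0) and two on placebo (0.038×48 = 1.8), against 95% half-widths near 13–14 points. SAP 3.4.2.3 gives event and censoring counts by arm, and SAP 3.3.1 tabulates withdrawals before Week 16.

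Most of this stands as a limit on size. It does not remove the problem. SAP 3.4.2.3 plans medians with intervals and a log-rank test, with no incidence at Week 16 or 28 and no difference with an interval. At a 30% event rate by Week 16 the 6 mg/kg median may not be reached. Disposition is not cross-tabulated with event status, and the sensitivity analysis in SAP 3.4.1 is optional.

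Three stronger readings are tempting. A reader might infer that both components are certainly understated; the denominator is not stated, and step 5 shows that exclusion errs the other way. A reader might infer that most of the gap is drop-out for disease as well; step 6 does not support that. A reader might take the 12.6 and 9.8 points as the error in viremia; they mainly reflect the composite's declared failure rule.

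**Conclusion.** The inconsistency is explicit in the addendum. On the mITT reading, viremia incidence is a lower bound and its gap to the composite is almost entirely drop-out. For CMV disease the mismatch exists, but drop-out may be the smaller part of the gap.

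In the main scenario the understatement is 2.1 points (6 mg/kg) and 3.8 points (placebo). With 5–20% leaving event-free under a constant drop-out hazard, it is about 0.8–3.5 and 2.0–8.1 points. All of this assumes the planning rates, drop-out independent of outcome, constant event hazards and viremia in nearly every event. The mismatch concerns leavers before Week 16 only; event-free patients leaving between Weeks 16 and 28 are failures in neither the Week 28 composite nor its components.

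This should be corrected in reporting. It leaves the primary endpoint's definition unchanged.

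**What to change.** 1. State the denominator for CMV viremia and CMV disease, and say whether event-free leavers are in it.
2. Report Kaplan-Meier incidence of CMV viremia at Weeks 16 and 28 by arm, with the difference and 95% CI, censoring event-free leavers at the last CMV assessment. The data are already derived for SAP 3.4.2.3; these estimates are new.
3. Beside the composite, split failures by arm into observed CMV events and discontinuations counted as failures. Add a note to the supportive central-PCR analysis that it counts leavers as failures.
4. For CMV disease, report the observed count and treat any Kaplan-Meier estimate as supportive. Under Protocol 6.6 viremic patients may receive rescue treatment and finish the study early, so censoring them may be informative.

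Cost: a few table rows, reliance on independent censoring, and slightly higher reported viremia incidence. SAP 3.4.2.3 dates events by Rescue Phase entry, which should be footnoted where it affects the Week 16 cut.
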